8.4 Demographic and Other Baseline Characteristics

Demographic and baseline characteristics will be summarized using Intent-to-Treat (ITT) Population by treatment groups.

Age (years), height at screening (cm), body weight at screening (kg), and body mass index (BMI) at screening in kg/m^2 will be summarized using descriptive statistics and gender, race, and ethnicity will be summarized using frequencies and percentages.

Medical history will be summarized by frequencies and percentages of subjects by system organ class (SOC) and preferred term (PT), within SOC and PT sorted by descending frequencies. Subjects with multiple events for the same SOC or PT, will be counted only once for that SOC or PT. Medical history will be coded using MedDRA version 19.0.

Birth control methods will be summarized by frequencies and percentages.

All demographic and baseline characteristics described within this section will be presented in subject listings.

8.5 Prior and Concomitant Therapy

The World Health Organization (WHO) Drug Dictionary (March 2016) will be used to classify prior and concomitant medications by Preferred Name and WHO anatomical therapeutic chemical (ATC) classification of ingredients.

Prior medications are defined as any medication given prior to and stopped before the initial application of study medication. Concomitant medications are defined as any medication given to the subject starting on or after the day of the initial application of study medication or started prior to the initial application of study medication and continuing during the study.

If the start date of medication is unknown and the end date is known, then the medication will be considered:

- Prior to study medication if the end date is prior to the initial application of the study medication
- Concomitant to study medication if the end date is either on or after the initial application of study medication or the end date is unknown.

If both the start and end dates are unknown, then the medication will be considered to be “concomitant on-treatment”. The partial and completely missing dates for prior and concomitant medications will be imputed as mentioned in section 7.3.

Prior and concomitant medication will be summarized by frequencies and percentages of subjects by preferred name within each ATC, with ATC and preferred names sorted by descending frequency.

ATC classification level 2 will be used in summary tables and listings. If ATC classification level 2 is missing, then ATC classification level 1 will be used.

A subject listing of prior and concomitant medications will be presented.

8.6 Analysis of Efficacy Parameters

8.6.1 *Equivalence of Clinical Endpoint Analysis*

The primary efficacy analysis is to demonstrate that Acyclovir Cream, 5% - Perrigo (Test) is bioequivalent to Zovirax[®] Cream 5% - Valeant Pharmaceuticals (Reference).

The hypothesis to test bioequivalence of Test formulation to Reference formulation will be:

$$H_0 \text{ (null hypothesis): } \mu_T / \mu_R \leq 0.80 \text{ or } \mu_T / \mu_R \geq 1.25$$

versus

$$H_1 \text{ (alternative hypothesis): } 0.80 < \mu_T / \mu_R < 1.25$$

Where, μ_T : The mean time-to-complete healing of the lesion in the test treatment (i.e. Acyclovir Cream, 5% - Perrigo)

μ_R : The mean time-to-complete healing of the lesion in the reference treatment (i.e. Zovirax Cream 5% - Valeant Pharmaceuticals)

The test formulation (i.e. Acyclovir Cream, 5% - Perrigo) will be considered as bioequivalent to the reference formulation (i.e. Zovirax[®] Cream 5% - Valeant Pharmaceuticals) if the 90% confidence interval (CI) for the ratio of the means or medians (Test/Reference) falls within the interval of 0.80 to 1.25.

The mean time-to-complete healing of Test and Reference product will be analyzed using Analysis of Variance (ANOVA) with treatment and center as fixed effects in the model. The 90% confidence interval for the ratio (Test/Reference) of mean time-to-complete healing will be obtained by Fieller’s method.

A plot for the ratio (Test/Reference) of mean time-to-complete healing and associated 90% CI will be presented.

[REDACTED]

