8.4 Measures and Analysis

8.4.1 Efficacy Endpoint and Analysis

The primary efficacy endpoint will be the time to complete healing of lesions (defined as loss of crust and re-epithelialization with or without erythema, as assessed by the investigator, based on both clinical observation and review of the subject diary), measured in days/hours from the time of first dosing.

Equivalence of Clinical Endpoint Analysis

The mean time to complete healing of the lesion for the test and reference treatments will be estimated using analysis of Variance (ANOVA) with treatment and center as fixed effects in the model. The 90% confidence interval for the ratio (Test/Reference) of mean time-to-complete healing will be obtained by Fieller's method. A plot for the ratio (Test/Reference) of mean time-to-complete healing and associated 90% CI will be presented. For the time to complete healing of lesion the Test treatment will be considered to be therapeutically equivalent to the Reference treatment if the calculated 90% confidence interval of the ratio of the means (Test/Reference) falls within the interval of 0.80 to 1.25. Therapeutic equivalent evaluations in the per-protocol (PP) population will be considered the definitive analysis. This analysis will be repeated in the mITT population and will be considered the supportive analysis. Refer to the statistical analysis plan for analysis details.

Analysis of Superiority between active formulation and vehicle

Protocol No: PRG-NY-14-008

For the time to complete healing of the lesion, subjects who received active treatment will be compared to those who received the Vehicle as treatment in order to determine if superior efficacy has been attained.

The time-to-complete healing of both the active products and Vehicle will be analyzed using Analysis of Variance (ANOVA) evaluations with treatment and center as fixed effects in the model.

Each active treatment group will be compared to the Vehicle group using a -two-sided test and tested at an alpha level of 0.05. The mean and its 95% confidence interval will be reported.

Superiority will be considered demonstrated if the means for both active treatments are statistically different from ($p < 0.05$), and smaller than, that for the Vehicle

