4.2 Discussion of Study Design

This study is designed to demonstrate the bioequivalence of Perrigo's Acyclovir Cream, 5% to Valeant's Zovirax[®] Cream 5% and will also demonstrate the superiority of efficacy of Perrigo's Acyclovir Cream, 5% and Valeant's Zovirax[®] Cream 5% over Perrigo's Vehicle of Acyclovir Cream, 5%. This study has the following design characteristics:

- Randomized: This is done in order to eliminate the allocation bias and balancing both known and unknown prognostic factors, in the assignment of treatments.
- Vehicle control (Placebo): This study involves a Vehicle group that will be used to demonstrate the superiority of the test and reference formulations.
- Bioequivalence: To establish bioequivalence between Perrigo's Acyclovir Cream, 5% (test) and Valeant's Zovirax[®] Cream 5% (reference), the 90% confidence interval of the test/reference ratio for the primary endpoint, time-to lesion healing, must be contained within [0.80, 1.25]
- Superiority: As per the FDA guidelines, if bioequivalence is demonstrated for test and reference formulations, this will only be accepted if the study had adequate sensitivity to detect true differences between formulations if they existed. Hence, this study is designed to demonstrate the superiority of Perrigo's Acyclovir Cream, 5% and Valeant's Zovirax[®] Cream 5% over Perrigo UK FINCO's Vehicle of Acyclovir Cream, 5%.

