7.6 Multiple Comparisons/Multiplicity

Not applicable to this study.

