7.8 Active-Control Studies Intended to Show Equivalence

The objective of this study is to demonstrate the bioequivalence of Perrigo’s Acyclovir Cream, 5% (Test) to Valeant’s Zovirax[®] Cream 5% (Reference), assessed by mean time-to-complete healing of the lesion. For the purpose of bioequivalence testing, the 90% confidence interval (CI) of the ratio of the means (Test/Reference) must fall within the interval of 0.80 to 1.25.

In addition to testing bioequivalence, the superiority of efficacy of Perrigo’s Acyclovir Cream, 5% (Active) and Valeant’s Zovirax[®] Cream 5% (Active) over Perrigo’s Vehicle of Acyclovir Cream, 5% (Vehicle) will be demonstrated by comparing the mean time-to-complete healing of lesion of the active treatments to that for the vehicle control. Superiority will be considered demonstrated if the means for both active treatments are statistically different from ($p < 0.05$), and smaller than, that for the Vehicle

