8.6.4.2 Analysis of Superiority between Active Formulation and Vehicle in Time-to-Event

If the residuals diagnostic from the ANOVA (section 8.6.2) does not demonstrate homogeneity of variance, non-parametric analyses will be performed. A non-parametric ANOVA controlling for Center (Stoke, 2000¹⁰), will be done to test the superiority of the Reference vs. Vehicle and of the Test vs. Vehicle ($p < 0.025$).

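### SAP 8.6.1 lets the primary equivalence claim rest on a ratio of means or of medians, although the hypotheses, the confidence interval method and the protocol are for means only

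*SAP*

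**What the plan says.** SAP 8.6.1 sets the null and alternative hypotheses on μT/μR with limits 0.80 and 1.25. It defines the numerator as "The mean time-to-complete healing of the lesion in the test treatment", and the reference parameter likewise as a mean. The decision sentence follows and is met if the "90% confidence interval (CI) for the ratio of the means or medians (Test/Reference) falls within the interval of 0.80 to 1.25". The section then returns to means: an ANOVA with treatment and center as fixed effects, and "The 90% confidence interval for the ratio (Test/Reference) of mean time-to-complete healing will be obtained by Fieller"'s method, with a plot of the same ratio.

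The other statements of the rule are:

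- **SAP 7.8:** "the 90% confidence interval (CI) of the ratio of the means (Test/Reference) must fall within the interval of 0.80 to 1.25".
- **Protocol 8.4.1**, and the synopsis in the same terms: the "calculated 90% confidence interval of the ratio of the means (Test/Reference) falls within the interval of 0.80 to 1.25". Protocol 8.4.1 makes the per-protocol population definitive for this comparison.
- **SAP 4.2:** "the 90% confidence interval of the test/reference ratio for the primary endpoint, time-to lesion healing, must be contained within [0.80, 1.25"; it names neither means nor medians.

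SAP 7.6, on multiplicity, reads "Not applicable to this study". The readable text does not say when a median would apply, how its interval would be computed, or which statistic governs if the two disagree. The end of 8.6.1, SAP 5.2 (changes from the protocol analyses) and the body of 8.6.4.1 (exploratory equivalence analysis) are not readable.

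**The concern.** This sentence is the trial's pass/fail rule, and it names two different parameters joined by *or*. The mean and median ratios agree when one arm's distribution is a rescaled copy of the other's. They can differ when the arms differ in spread or in the share of slow healers.

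Two problems follow from the literal reading. First, two intervals each get a chance to pass, with no adjustment. Second, a pass on the median alone would be reported as rejecting a null hypothesis about means that it does not test. If the two results disagreed, the sponsor would have to choose between them after seeing the data, and a regulator could fairly call that choice data-driven.

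**Working it through.** **Step 1: the text.** Each place that states or implements the rule, by statistic:

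| Place | Statistic |
|---|---|
| SAP 8.6.1, hypotheses | mean |
| SAP 8.6.1, decision sentence | mean or median |
| SAP 8.6.1, model, interval and plot | mean |
| SAP 7.8 | mean |
| Protocol 8.4.1 and synopsis | mean |
| SAP 4.2 | not named |

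Only the decision sentence mentions medians. The contradiction needs no arithmetic.

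**Step 2: the nominal level.** The readable documents give no sample size, power or SD to reproduce. The level can be checked: a 90% interval inside 0.80 to 1.25 is two one-sided tests at (1 − 0.90)/2 = 0.05 each. If either of two intervals may pass, the false-equivalence rate with both true ratios on a limit is at most 0.05 + 0.05 = 0.10.

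**Step 3: either-or rule, same shape in both arms.** Two simulations, both without center effects and with assumed inputs:

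- *A.* Lognormal times, reference mean 8 days, SD 3 or 4 days, 100, 150 or 250 per arm, true ratio 1.25 or 0.80, 4,000 runs per setting. Fieller interval for means, percentile bootstrap (500 resamples) for medians.
- *B.* Lognormal or gamma times, CV 0.4 to 0.6, 100, 200 or 300 per arm, true ratio 1.25, 20,000 runs per setting. Fieller interval for means, Price-Bonett interval on the log scale for medians.

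| | Means only | Either may pass |
|---|---|---|
| A | 4.3% to 5.2% | 6.5% to 7.9% |
| B | 4.5% to 5.1% | 7.3% to 8.1% |

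P(either) = P(mean) + P(median) − P(both). For example, in B with lognormal times, CV 0.5 and 200 per arm: 0.0482 + 0.0488 − 0.0196 = 0.0774.

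**Step 4: conditional readings.** Suppose one statistic is chosen by a residual check, again with same-shape lognormal times.

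- With a Shapiro-Wilk normality trigger, false equivalence was 3.8% to 4.7%. Normality was rejected almost always, so the claim then rested on medians.
- With a variance-homogeneity trigger (Levene, p < 0.05), the kind of check SAP 8.6.4.2 uses for superiority, it was 5.2% to 7.1%.

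**Step 5: unequal spread.** For lognormal arms, median ratio = mean ratio × √[(1 + CV_R²)/(1 + CV_T²)]. With the mean ratio held at 1.25, on the null boundary:

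| CV, test vs reference | Median ratio | Means only | Either may pass (100 to 300 per arm) |
|---|---|---|---|
| 0.6 vs 0.5 | 1.25 × √(1.25/1.36) = 1.198 | 4.9% to 5.3% | 14% to 21% |
| 0.6 vs 0.4 | 1.25 × √(1.16/1.36) = 1.154 | 4.8% to 5.2% | 24% to 49% |
| 0.7 vs 0.4 | 1.25 × √(1.16/1.49) = 1.103 | 4.9% to 5.5% | 36% to 75% |

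A second illustration made 20% or 30% of test-arm subjects slow healers and capped times at Day 21, with the capped mean ratio at 1.25 and 150 or 250 per arm. It gave 11% to 72%. Most of the excess in these illustrations comes from the median interval passing alone. That is an estimand mismatch rather than a multiplicity effect.

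**The case against.** The strongest reply is that the supposed gap lies where text is blacked out. SAP 8.6.1 breaks off in a redaction directly after the plot sentence, and SAP 5.2 and the body of 8.6.4.1 cannot be read. The SAP reference list has five bootstrap entries with no visible citation, so a planned bootstrap interval for medians is plausible. The parallel superiority section is conditional: "If the residuals diagnostic from the ANOVA (section 8.6.2) does not demonstrate homogeneity of variance, non-parametric analyses will be performed". Protocol 8.1 and 8.4.1 defer analysis detail to the SAP, so a median fallback declared in SAP 5.2 could be a documented change. As readable, only one interval can be computed, the Fieller interval for means.

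Much of this stands. It cannot be said that the plan lacks a median method or that a second chance was intended. The figures in step 5 depend on shapes that no document supports and are not expected error rates. The absence of inflation in step 4 belongs to the normality trigger alone. Deleting the words without reading the hidden text could also orphan a pre-specified fallback.

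The objection does not remove the conflict. A hidden condition would leave the decision sentence unconditional, beside hypotheses about means and at odds with SAP 7.8 in the same document. Section 8.6.4.1 is listed under exploratory analyses, and an exploratory statistic does not belong in the primary decision sentence. The protocol fixes the ratio of means as the criterion itself, which is more than an analysis detail.

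**Conclusion.** The concern holds. The primary decision sentence in SAP 8.6.1 contradicts the hypotheses and interval method in its own section, SAP 7.8 and the protocol. Confidence is high because this rests on the text alone.

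The practical size is less certain. On the either-or reading with arms of the same shape, false equivalence rises by roughly 2 to 3 percentage points above means only, and cannot exceed 10% when each test holds its 5% level. If the arms differ in shape or spread, the error against the mean-based null can be several times the nominal 5%. If redacted text makes the median conditional, inflation ranges from none to about 2 points under the two triggers tried, but the claim may then concern a parameter the hypotheses do not mention. All these figures depend on assumed distributions, sample sizes and median interval methods, and the trial's actual censoring rule is not visible. Because the sentence decides the trial's conclusion, it should be corrected before unblinding.

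**What to change.** Delete *or medians* from the decision sentence in SAP 8.6.1. Equivalence then rests on the Fieller 90% interval for the ratio of means in the per-protocol population, and any median ratio is labelled exploratory.

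If a median fallback is already specified in text not readable here, do not simply delete the words. State one definitive statistic, the objective trigger for any switch and the interval method for medians. Bring the hypotheses in SAP 8.6.1, SAP 7.8 and Protocol 8.4.1 with its synopsis into line before unblinding.

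The first route costs two words, the second a short paragraph and matching edits. Neither needs new data. Dropping the either-or option also gives up some chance of passing. In simulation B at a true ratio of 1.0, the largest loss was 76.0% − 66.4% = 9.6 points (lognormal, CV 0.6, 100 per arm), and it was under 2 points in every setting with 200 or more per arm.

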8.6.1.1 Sensitivity Analysis Using Secondary Censoring Rule for Aborted Lesions

[REDACTED]

[REDACTED]

8.6.1.2 Sensitivity Analysis Exclusion of Sites/Subjects

[REDACTED]

[REDACTED]

8.6.2 Analysis of Superiority between Active Formulation and Vehicle

The test for superiority will be performed to show each of the active formulations (i.e. Acyclovir Cream, 5% - Perrigo and Zovirax® Cream 5% - Valeant Pharmaceuticals) is superior in efficacy over Vehicle of Acyclovir Cream, 5% - Perrigo.

The hypothesis to test the superiority of active formulations over vehicle will be:

$$H_{0t}: \mu_T \geq \mu_P \text{ vs } H_{1t}: \mu_T < \mu_P$$

$$H_{0r}: \mu_R \geq \mu_P \text{ vs } H_{1r}: \mu_R < \mu_P$$

Where,

[REDACTED]

μ_T : The mean time-to-complete healing of the lesion in the test i.e. Acyclovir Cream, 5% - Perrigo

μ_R : The mean time-to-complete healing of the lesion in the reference i.e. Zovirax Cream 5% - Valeant Pharmaceuticals

μ_P : The mean time-to-complete healing of the lesion in the Vehicle

Two separate superiority analyses will be conducted, Test vs. Vehicle and Reference vs. Vehicle. The mITT Population will serve as the definitive analysis, and analysis based on the PP Population will be considered as the supportive one for the superiority analysis.

The time-to-complete healing of both the active products and Vehicle will be analyzed using Analysis of Variance (ANOVA) evaluations with treatment and center as fixed effects in the model.

The statistical significance (p-value) of mean time-to-complete healing of Test vs. Vehicle and Reference vs. Vehicle will be determined identically using separate ANOVA tests. The difference in adjusted mean (LS means) time-to-complete healing between active products and Vehicle, and the associated 95% CIs of the difference will be presented.

8.6.2.1 Sensitivity Analysis Using Secondary Censoring Rule for Aborted Lesions

[REDACTED]

[REDACTED]

8.6.2.2 Sensitivity Analysis Exclusion of Sites/Subjects

[REDACTED]

[REDACTED]

[REDACTED]

8.6.3 Subgroup Analyses

No subgroup analyses of efficacy data are planned.

8.6.4 Exploratory Analyses

The elapsed time, in hours, between the subject-reported lesion healing date/time and the investigator-assessed lesion healing date/time will be summarized.

The elapsed time is calculated as investigator date/time minus subject date/time.

[REDACTED]

[REDACTED]

[REDACTED]

[REDACTED]

[REDACTED]

[REDACTED]

[REDACTED]

8.6.4.2 Analysis of Superiority between Active Formulation and Vehicle in Time-to-Event

If the residuals diagnostic from the ANOVA (section 8.6.2) does not demonstrate homogeneity of variance, non-parametric analyses will be performed. A non-parametric ANOVA controlling for Center (Stoke, 2000¹⁰), will be done to test the superiority of the Reference vs. Vehicle and of the Test vs. Vehicle ($p < 0.025$).

8.6.5 Other Efficacy Analyses

[REDACTED]

8.7 Analysis of Safety

All safety analyses will be performed using the safety population and will be summarized by treatment groups. No statistical inference will be drawn on safety analyses.

Due to the nature of the safety population (all subjects dispensed medication), analyses will be based on all subjects who were dispensed medication. For example, TEAE percentages are based on all subject dispensed medication (includes dosed and not dosed subjects).

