5.8 Study Medication Use, and Diary Instructions

At the Screening Visit (Visit 1), each subject will be screened for inclusion/exclusion criteria. The subjects who qualify will be randomized and dispensed the study medication along with the diary including the study instructions.

The study staff will instruct the subject how to apply the study medication.

Protocol No: PRG-NY-14-008

[REDACTED]

The study staff will also instruct the subject on how to complete the diary. The subjects will record the time and date of each application and healing time in the diary. Subjects will be asked to record the stage of their herpes lesion as well as record their symptoms (i.e. pain, burning, stinging, itching, tingling, etc.) twice a day. [REDACTED]

The subject will be instructed to bring the diary and study medication with them at all visits for staff review of compliance. The study staff must confirm that the subject is recording all relevant information in a proper manner.

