8.4.2 Safety Endpoints and Analysis

The safety population will be used in the safety analyses.

All AEs will be classified with respect to system organ class (SOC) and preferred term using MedDRA. A treatment-emergent AE is an event that occurs or worsens after the administration of first dose of study medication. The AE profile will be characterized with severity and attribution (unrelated and related) to study medication. Related AEs will be events that are definitely, possibly or probably related to treatment in the investigator's judgment.

The number and percent of patients who report treatment-emergent AEs will be summarized for each treatment group. Additional summaries by severity and relationship to study medication will be presented for each treatment group. In addition, the number and percent of patients who reported treatment-emergent AEs of interest and serious AEs will be summarized for each treatment group.

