6.5.2 Adverse Events

All adverse events (AEs) occurring after signing the informed consent are to be recorded on the AE pages of the eCRF. All AEs will be classified with respect to system organ class and preferred term using MedDRA version 19.0.

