6.5.2.1 Definitions

Adverse event (AE)

An adverse event (AE) is any untoward medical occurrence in a subject administered a medicinal product and which does not necessarily have to have a causal relationship with this treatment. An adverse event can therefore be any unfavorable and unintended sign (for example, an abnormal laboratory finding), symptom, or disease temporally associated with the use of a medicinal product, whether or not considered related to this medicinal product.

Serious adverse event (SAE)

Any untoward medical occurrence that meets any of the following criteria:

- Results in death
- Life-threatening event
- Requires in-subject hospitalization or prolongation of existing hospitalization
- Results in persistent or significant disability or incapacity or substantial disruption of the ability to conduct normal life functions
- Results in a congenital abnormality or birth defect
- Any other adverse events that may be considered serious based upon medical judgment

Unexpected adverse event

An unexpected event is any adverse drug experience, the specificity or severity of which is not consistent with the current approved product labeling (package insert) for the study

[REDACTED]

medication, the Investigator's Brochure, or as described in the clinical protocol and consent materials.

Treatment emergent adverse event (TEAE)

Treatment-emergent adverse events (TEAE) are any AEs that occur or worsen (increase in severity and/or frequency) during or after the initial application of the study medication.

For treatment-emergent status regarding events with partial or missing dates, please refer to Section 7.3.

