7.3 Handling of Dropouts or Missing Data

All available data from subjects who discontinue from the study will be used. Subjects who discontinue the study prior to or after the initiation of the study medication will not be replaced.

For AEs with missing severity, the most severe assessment will be imputed for summary analyses. Any missing causal relationship of an AE to study medication will be summarized as related.

For analyses, partial and completely missing start dates for adverse events and concomitant medications should be imputed as follows:

[Redacted]

[Redacted]	[Redacted]	[Redacted]	[Redacted]	[Redacted]
[Redacted]	[Redacted]	[Redacted]	[Redacted]	[Redacted]

[REDACTED]	[REDACTED]	[REDACTED]	[REDACTED]	[REDACTED]
[REDACTED]	[REDACTED]	[REDACTED]	[REDACTED]	[REDACTED]
[REDACTED]	[REDACTED]	[REDACTED]	[REDACTED]	[REDACTED]
[REDACTED]	[REDACTED]	[REDACTED]	[REDACTED]	[REDACTED]

[REDACTED]

[REDACTED]

- [REDACTED]
- [REDACTED]

[REDACTED]

[REDACTED]

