Safety	
Subjects who were randomized, and dispensed the study medication regardless if the medication was used or not by the subject. Subjects will be summarized according to the actual treatment dispensed.
	
The safety displays will use this population which includes (Exposure, AE, application site reaction, physical examinations and vital signs)

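### TEAE percentages are divided by all dispensed subjects, dosed or not, so each understates incidence among dosed subjects by the undosed share of the arm

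*SAP*

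**What the plan says.** **Denominator.** SAP 8.7 gives TEAEs as its own example: "TEAE percentages are based on all subject dispensed medication (includes dosed and not dosed subjects". SAP 8.3, Table 5, defines the Safety population as "Subjects who were randomized, and dispensed the study medication regardless if the medication was used or not by the subject". Protocol 8.2 has a single ITT/Safety definition that asks only for randomization and receipt of medication; its mITT definition adds use of at least one dose.

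**Numerator.** SAP 6.5.2.1 requires a TEAE to start or worsen "during or after the initial application of the study medication". Protocol 8.4.2 agrees: "A treatment-emergent AE is an event that occurs or worsens after the administration of first dose of study medication". SAP 8.7.2 restricts AE summary tables to TEAEs by default. AE collection starts earlier (SAP 6.5.2): "All adverse events (AEs) occurring after signing the informed consent are to be recorded on the AE pages of the eCRF". For incomplete dates, SAP 6.5.2.1 adds: "For treatment-emergent status regarding events with partial or missing dates, please refer to Section 7.3". The rules in 7.3 are redacted.

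**Dispensing.** Protocol 5.8 places dispensing at the screening visit: "The subjects who qualify will be randomized and dispensed the study medication along with the diary including the study instructions". Exclusion criterion 9 (Protocol 4.2) bars anyone whose current episode has not fully healed. SAP Table 3 sets Day 1 as the date of first application. SAP 7.3 foresees withdrawal before any use: "Subjects who discontinue the study prior to or after the initiation of the study medication will not be replaced".

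**The concern.** A subject who never applies the cream can have an adverse event on record, because collection starts at consent. By definition that event is not treatment-emergent. Such a subject adds one to the denominator of every TEAE percentage and nothing to the numerator.

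Undosed subjects are foreseeable. The cream is handed out at screening to people without an unhealed episode, so use waits for a later recurrence that may not come. SAP 8.7 itself names undosed subjects.

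Protocol 2.2 compares test and reference partly on how often adverse events occur. A reader will normally take a TEAE percentage as incidence among people exposed to the product. The planned figure is lower than that by a relative u, and SAP 8.7.2 lists no second percentage restricted to dosed subjects.

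**Working it through.** The plan states no figure on this point, so there is nothing to reproduce. The check is an identity within one arm.

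**Inputs**
- N: subjects dispensed medication, the planned denominator (SAP 8.7; Table 5, Safety).
- D: subjects with at least one application. Date and time of first application are listed under SAP 8.7.1.1.
- x: subjects with a given TEAE, all of them among the D dosed subjects (SAP 6.5.2.1; Protocol 8.4.2).
- u = (N - D)/N. The documents give no value; every u and event rate below is an assumption.

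**Identity**

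x/N = (x/D) × (D/N) = (x/D) × (1 - u)

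Example with N = 100, D = 70, x = 7: u = 30/100 = 0.30. The rate among dosed subjects is 7/70 = 10.0%. The planned percentage is 7/100 = 7.0%, and 10.0 × 0.70 = 7.0.

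**Size over a range of u**

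| Assumed u | 10% among dosed prints as | 5% among dosed prints as | Difference of 5 points prints as | Ratio, equal u | Factor back to dosed rate, 1/(1-u) |
|---|---|---|---|---|---|
| 0 | 10.0% | 5.0% | 5.0 points | 2.0 | 1.00 |
| 10% | 9.0% | 4.5% | 4.5 points | 2.0 | 1.11 |
| 30% | 7.0% | 3.5% | 3.5 points | 2.0 | 1.43 |
| 50% | 5.0% | 2.5% | 2.5 points | 2.0 | 2.00 |

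**Unequal u.** The test/reference ratio is multiplied by (1 - uT)/(1 - uR). With uT = 0.35 and uR = 0.25 this is 0.65/0.75 = 0.867; with the values swapped it is 0.75/0.65 = 1.154.

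**Smallest visible effect.** SAP 7.1 prints percentages to one decimal. A shift of 0.1 point needs u = 0.1/rate: 0.1/10 = 1% for a 10% rate, 0.1/5 = 2% for a 5% rate and 0.1/2 = 5% for a 2% rate. A small u can change a printed figure, but a change of that size is minor.

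**Where the identity could fail.** If date imputation classed an event in one undosed subject as a TEAE, the example would print (7 + 1)/100 = 8.0% instead of 7.0%. The redacted rules in SAP 7.3 decide whether this can happen.

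**Scope.** The identity covers subject-level rows defined as TEAEs. It does not cover event counts, the unexpected-adverse-event rows (not worded as TEAEs) or the application-site-reaction tables.

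**The case against.** The strongest reply is that this is a disclosed and consistent choice. SAP 8.7 states the denominator outright, Table 5 matches it, and the protocol's Safety definition does not contradict it. No inference is drawn from safety data. Never using the cream is settled before any exposure, and the kits are randomized and blinded, so product effects cannot drive u; arms should differ in u only by chance or incidental factors. SAP 8.1 reports numbers treated by arm, so a reader could rescale.

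Most of this stands and limits the harm. Three parts do not remove the point:
- Disclosure in the SAP does not change the percentages printed in the tables.
- Where safety is only descriptive, the percentages carry the comparison.
- Rescaling from SAP 8.1 is approximate. Table 5 assigns disposition displays to the ITT set by randomized treatment, and safety displays to the treatment actually dispensed. Randomized minus treated is also not strictly dispensed minus dosed, since SAP 8.7.1.3 lists dispensing as its own item.

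A reader might infer that the safety comparison of test with reference is biased. The documents do not support that: with equal u the ratio is untouched, and nothing suggests that u differs by arm. Nor do they support a claim that SAP 7.3 lacks a rule for undosed subjects, because its imputation rules are blacked out.

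**Conclusion.** The point holds as a modest one. As written, the plan will print TEAE percentages that understate incidence among dosed subjects by a relative u, and will shrink absolute differences between arms by the factor (1-u) when u is equal. The ratio between arms moves only if u differs.

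This rests on two conditions: the redacted imputation rules do not turn an event in an undosed subject into a TEAE, and some dispensed subjects go undosed. The design makes the second plausible, but the size is unknown; if everyone is dosed, the effect is zero. A reader might take the 50% row of the table as a forecast that rates will be halved. It is an illustration only, and nothing in the documents supports that value over a small one.

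**What to change.** Change SAP 8.7 so that TEAE percentages use subjects with at least one recorded application as the denominator. At minimum, keep the planned percentage and print beside it the dosed-subject percentage, with the dosed N per arm.

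In either case, show dosed and dispensed-but-not-dosed counts by arm. Derive them from the dispensing record (SAP 8.7.1.3) and the date and time of first application (SAP 8.7.1.1), not from randomized minus treated.

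Leave the ITT/Safety definition, the other safety displays and SAP 7.3 as they are. Redefining the Safety set would split the protocol's single ITT/Safety definition and would also alter the exposure, application-site-reaction, physical-examination and vital-sign displays that use it.

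The cost is a revised sentence in SAP 8.7, minor programming on data already listed and, for the side-by-side version, one extra column per arm. Percentages on the dosed denominator will be higher by 1/(1-u). Protocol 8.4.2 names the safety population for safety analyses, so replacing the denominator outright should be recorded as a change from the protocol; the side-by-side version keeps the planned figure. Either should be settled before unblinding.
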